
Statistical methods:
	
The primary model will be a Wilcoxon rank test on change from baseline to week 12 in 6MWT.
 
The primary model will be conducted on all randomized patients.
 
Both key secondary endpoints will be tested using a Wilcoxon rank test, and both will be tested if the primary endpoint revealed a significant result in favour of empagliflozin. For adjustment of multiplicity of the two key secondary endpoints a Hochberg procedure will be followed.
 
The other secondary endpoints will not be part of the testing hierarchy.
 
Change from baseline to week 6 in exercise capacity as measured by the distance walked in 6 minutes will be evaluated using the same model as for the primary endpoint
 
Change from baseline to week 12 of Clinical Congestion Score will be evaluated using a mixed model repeated measure analysis over time. The model will include the factor treatment and the linear covariate of baseline Clinical Congestion Score.
 
Proportion of patients in every category of global impression of change at week 12 will be evaluated using Cochran-Mantel-Haenszel test.
 
Proportions of patients categorized by the shift in scores between baseline and week 12 in patient global impression of severity score will be evaluated using Cochran-Mantel-Haenszel test.

	The endpoint “Change from baseline in NT-proBNP at week 12” (after log-transformation) will be evaluated using a mixed model repeated measure analysis over time with baseline log-transformed NT-proBNP as a covariate without imputation of missing values.
--	---

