## FLOW CHART

Trial Period	Screening*	Randomized Treatment Period				FU Period
		1	2	3	4 (EOT)	
Visit	1	2	3	4 (EOT)	Early Discontinuation on Visit 	FU Visit
Trial week	-3	1	6	12		EOT/early d/c + 7 days
Days of treatment	-21 to -4	1	43	85		
Time Window	-	-	±7	±7		+7
Informed consent	X					
In/exclusion criteria	X	X				
Demographics	X					
Medical history/Concomitant diagnoses	X					
Vital signs 	X	X	X	X	X	X
Physical examination	X	X		X	X	
Height	X					
Weight	X	X		X	X	
Urine Pregnancy test 	X	X	X	X	X	
HbA1c		X		X	X	
eGFR (CKD-EPIcr formula)	X 	X	X	X	X	X
Safety lab: blood tests	X 3*	X	X 	X	X	X
Safety lab: urinalysis including ketones	X 	X	X	X	X	X
ECG exam 	X 			X	X	
Echocardiogram 	X					
NT-proBNP	X 	X	X	X	X	
6 min walk test 	X 	X 	X	X 	X	
Concomitant therapy	X	X	X	X	X	X
Adverse events	X	X	X	X	X	X
KCCQ 		X	X	X	X	
CHQ-SAS 		X	X	X	X	
Clinical Congestion Score		X	X	X	X	
Patient Global Impression of Severity of Heart Failure Symptoms 		X	X	X	X	
Patient Global Impression of Severity of Dyspnea 		X	X	X	X	
Patient Global Impression of Change in Heart Failure Symptoms 			X	X	X	

Trial Period	Screening*	Randomized Treatment Period				FU Period
Visit	1	2	3	4 (EOT)	Early Discontinuation on Visit 	FU Visit
Trial week	-3	1	6	12		EOT/early d/c + 7 days
Days of treatment	-21 to -4	1	43	85		
Time Window	-	-	±7	±7		+7
Patient Global Impression of Change in Dyspnea 			X	X	X	
Clinician Global Impression of Severity of CHF		X	X	X	X	
Clinician Global Impression of Change in CHF Severity			X	X	X	
NYHA Classification	X	X	X	X	X	
HCRU		X	X	X	X	
Randomization (IRT)		X				
Dispense trial medication		X	X			
Return medication / Medication compliance check			X	X	X	

\* The screening procedures can be performed on different days within the time window. Specifically it is recommended to have the NT-proBNP and safety lab measures (via central lab) measured as first step, especially in patients with no previous natriuretic peptide value available from clinical routine assessment in the past 6 months (refer to [section 6.2.1](#)). The baseline rhythm (e.g. sinus rhythm, AF) of the patient must be clarified (i.e. ECG) and documented at the time the NT-proBNP sample is collected.

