### 3.3.2 Inclusion criteria

1. Of full age of consent (according to local legislation, usually  $\geq 18$  years) at screening.
2. Male or female patients. Women of childbearing potential (WOCBP) must be ready and able to use highly effective methods of birth control per ICH M3 (R2) that result in a low failure rate of less than 1% per year when used consistently and correctly. A list of contraception methods meeting these criteria is provided in the patient information. For sites in Portugal please refer to the contraception methods described in [appendix 10.7](#).
3. Signed and dated written informed consent in accordance with ICH-GCP and local legislation prior to admission to the trial
4. 6MWT distance  $\leq 350$  m at screening and at baseline.

---

 A woman is considered of childbearing potential (WOCBP), i.e. fertile, following menarche and until becoming post-menopausal unless permanently sterile.

A postmenopausal state is defined as no menses for 12 months without an alternative medical cause.

Permanent sterilisation methods include hysterectomy, bilateral salpingectomy and bilateral oophorectomy.

Please note that tubal ligation is NOT accepted as a method of permanent sterilisation and therefore a woman who underwent tubal ligation is still considered as WOCBP. However tubal ligation is considered as a method of highly effective birth control.

5. Patients with chronic HF diagnosed for at least 3 months before Visit 1 and currently in NYHA class II-IV
6. Chronic HF with reduced EF defined as LVEF  $\leq 40\%$  as per echocardiography at Visit 1 as per local reading (obtained under stable condition).
7. Elevated NT-proBNP  $> 450$  pg/ml for patients without atrial fibrillation (AF) OR NT-proBNP  $> 600$  pg/ml for patients with AF as analysed at the Central laboratory at Visit 1
8. Patients must be clinically stable and on appropriate and stable dose of medical therapy for HF (such as ACEi, ARB,  $\beta$ -blocker, oral diuretics, MRA, ARNI, ivabradine), consistent with prevailing CV guidelines, stable for at least 4 weeks prior to Visit 1 (screening) with the exception of diuretics which must have been stable for at least two weeks prior to Visit 1. The investigator must document the reason in case the patient is not on such medication or if not on target dose of any heart failure medication as per local guidelines.

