### 5.1.4 NT-proBNP

Samples for NT-proBNP will be collected at Visit 1 (Screening) to determine whether the patient is eligible for the trial. Further samples for NT-proBNP will be collected at later time points in the trial (see [Flow Chart](#)) to investigate a potential effect of the trial medication. Samples for NT-proBNP will be analysed at the Central Laboratory.

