### 6.2.2 Treatment period(s)

Randomisation will occur at Visit 2 using IRT. The patients will return to the clinic for regularly scheduled visits 6 and 12 weeks after randomisation as specified in the [Flow Chart](#). These on-site visits will assess the occurrence of safety and efficacy endpoints, trial medication compliance, concomitant therapy or intervention.

All visit 2 assessments must be performed before the first dose is taken in the site. The assessments at visits 3 and 4 must be performed post-dose. Patients should be instructed to take their medication on the morning of trial visits 3 and 4. Visits should be routinely scheduled at approximately the same time of day for each visit.

At all treatment visits (visits 2, 3 and 4/EOT) and the early discontinuation visit, patient reported outcome measures should be completed first.

Patient reported outcome measures should be completed in the following order:

- KCCQ
- PGI – Severity – Heart Failure Symptoms
- PGI – Change – Heart Failure Symptoms
- PGI - Severity - Dyspnea
- PGI - Change – Dyspnea
- CHQ-SAS

The order of the remaining assessments should be preferably completed as follows and according to the visits specified in the [Flowchart](#):

- Physical examination, body weight, height and vital signs
- Completion of clinician impression scales and clinical congestion score by Investigator
- ECG
- 6MWT conducted in duplicate (at visits 2 and 4 only) at least 1 hour apart. At visits 1, 3 and the early discontinuation visit, only one 6MWT will be conducted.
- Laboratory sample, urine pregnancy

Testing of the 6MWT at each clinic visit should be performed about the same time of day to minimize intraday variability. Prior to performing the 6MWT the relative contraindications to exercise should be assessed as per [appendix 10.1.3](#).

All other medications the patient is receiving should be taken as instructed by the physician.

At any time during the treatment period the HF background therapy is allowed to be adjusted and optimised according to local and international guidelines.

If any additional therapy is considered necessary for the patient's welfare during the treatment period it may be given at the discretion of the Investigator (see also restrictions in [Section 4.2.2](#)).

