## 6.7 BASELINE, TIME WINDOWS AND CALCULATED VISITS

For serum creatinine and values based upon this measurement such as eGFR, baseline will be defined as the mean of all available measurements from the screening visit until start of randomised trial medication. For all other endpoints, baseline will be defined as the last available measurement before start of randomised trial medication.

Since the protocol specifies that all measurements are taken at visit 2 before any intake of trial medication, all measurements at the first day of drug intake are assumed to qualify as baseline measurements. For laboratory values, clock time is recorded. If a lab measurement is done after treatment start, this will not qualify as baseline measurements, except in case of HbA1c, which is considered to be a stable measurement and qualifies for baseline on the whole day of first treatment intake.

For randomised patients without any treatment intake: For serum creatinine and values based upon this measurement such as eGFR, baseline will be defined as the mean of all available measurements from the screening visit until and including the day of randomisation. For all other endpoints, baseline will be defined as the last available measurement before or on the day of randomisation.

Medication taken at baseline is any medication with start date continued or before date of first study medication intake (randomisation for patients not treated) and end date continued or on or after date of first medication intake (randomisation for patients not treated).

Measurements taken after the first intake of randomised trial medication will be considered on-treatment values if they have been obtained up to end of the parameter specific follow-up period as defined in [Table 6.7: 1](#) below and will be assigned to the randomised study drug for efficacy and safety analyses.

Measurements taken after the end of the endpoint specific follow-up period after the last intake of study drug will be considered post-treatment values.

On-treatment (for OC-OT analysis) or all post-randomisation (for OC-AD analysis) efficacy and safety measurements will be assigned to visits based on time windows around the planned visit dates. These time windows are defined based on the planned number of days after the date of first administration of study drug.

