### 7.5.2 Other Secondary endpoints

*Other secondary endpoints will not be part of the testing hierarchy.* No correction for multiple testing of the other secondary endpoints will be made.

*Change from baseline to week 6 in exercise capacity as measured by the distance walked in 6 minutes will be evaluated using the same model as for the primary endpoint.* If no 6MWTD is available at week 6, an imputed value as defined in [Section 6.6](#) will be used.

All other secondary endpoints will take into account all data, regardless of whether the patient was on treatment or not, and without imputation of missing values (OC-AD).

The other continuous endpoints are generally analysed in an MMRM, including visit-by-treatment interaction and baseline-by-visit interaction. An unstructured covariance structure will be used to model the within-patient errors. The MMRM analyses will also be shown graphically.

Descriptive statistics will be calculated for the value at visit and change from baseline.

Shift from baseline score to 12 week score will be tabulated descriptively for single items collected in the context of the clinical congestion score (dyspnea, orthopnea, fatigue, jugular venous distension, rales and edema).

The endpoint “Change from baseline in NT-proBNP at week 12” (after log-transformation) will be evaluated using an MMRM analysis over time with baseline log-transformed NT-proBNP by visit interaction and visit by treatment interaction as covariates without imputation of missing values. Estimates obtained from the model will then be back-transformed and reported on the original scale. The MMRM analyses will also be shown graphically.

Proportion of patients in every category of global impression of change at week 12 will be evaluated using Cochran-Mantel-Haenszel test on the difference in mean treatment scores, using modified ridit scores.

Proportions of patients categorised by the difference in scores between baseline and week 12 in patient global impression of severity score will be evaluated using a Cochran-Mantel-Haenszel test on the difference in mean treatment scores, using modified ridit scores. Difference in score will be defined as the number of categories improved/deteriorated from baseline. Shift from baseline score to 12 week score will be tabulated descriptively.

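### The NT-proBNP model adjusts only for the last pre-treatment value; adding the Visit 1 value already collected would probably tighten the interval for this exploratory endpoint at almost no cost

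*Protocol*

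**What the plan says.** **Sampling.** The protocol flow chart schedules NT-proBNP at Visit 1 (days -21 to -4), Visit 2 (day 1), Visits 3 and 4, and early discontinuation. The purpose of the first sample is stated in protocol 5.1.4: "Samples for NT-proBNP will be collected at Visit 1 (Screening) to determine whether the patient is eligible for the trial". Inclusion criterion 7 (protocol 3.3.2) applies a threshold of 450 pg/ml without atrial fibrillation, or 600 pg/ml with it, to the value "as analysed at the Central laboratory at Visit 1". The Visit 2 sample is also pre-treatment, because protocol 6.2.2 says: "All visit 2 assessments must be performed before the first dose is taken in the site".

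**Baseline.** SAP 6.7, in line with protocol 7.3, makes an exception for creatinine and eGFR, where "baseline will be defined as the mean of all available measurements from the screening visit until start of randomised trial medication". NT-proBNP falls under the general rule: "For all other endpoints, baseline will be defined as the last available measurement before start of randomised trial medication".

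**Model.** The protocol synopsis gives one baseline covariate on the log scale, in a "mixed model repeated measure analysis over time with baseline log-transformed NT-proBNP as a covariate without imputation of missing values", and protocol 7.3.2 repeats this. SAP 7.5.2 fits the MMRM "with baseline log-transformed NT-proBNP by visit interaction and visit by treatment interaction as covariates without imputation of missing values". No screening value appears in the model.

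**Status.** Protocol 7.2 and SAP 7.5.2 place this endpoint outside the testing hierarchy, with no multiplicity correction. Protocol 7.7 gives no power or precision figure for it.

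**The concern.** A single NT-proBNP sample reflects the patient's usual level plus visit-to-visit noise. Adjusting for one such sample leaves part of the stable between-patient difference in the error term. A second pre-randomisation sample from the same central laboratory helps to estimate that level, and entry criterion 7 means that essentially every randomised patient has one. When Visit 2 is available, the plan puts the Visit 1 value to no use in the model.

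At stake is the width of the confidence interval for the week 12 treatment effect, and for the week 6 effect from the same model. Because the plan sets no power for this endpoint, interval width is how readers will judge what the trial says about it.

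**Working it through.** **Plan's own figure.** There is none to reproduce. Protocol 7.7 covers the walk test, and 7.7.1 covers the two key secondary questionnaires. Neither document gives an SD or a correlation for NT-proBNP, so every correlation and SD below is an assumption.

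**Formula.** The week 12 contrast from an MMRM with unstructured covariance and a baseline-by-visit term is treated as an ANCOVA. On the log scale let a = corr(Visit 1, Visit 2), b = corr(Visit 2, week 12) and c = corr(Visit 1, week 12). The residual variance with both covariates, divided by that with Visit 2 alone, is

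ratio = 1 - (c - ab)² / [(1 - a²)(1 - b²)].

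The standard error changes by the square root of this ratio. If c = ab, the gain is zero. If all three correlations equal r, the ratio becomes (1 + 2r)/(1 + r)².

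**Equal correlations.**

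| r | variance falls | SE falls |
|---|---|---|
| 0.5 | 11% | 6% |
| 0.7 | 17% | 9% |
| 0.9 | 22% | 12% |

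For r = 0.7: 2.4/2.89 = 0.830, and its square root is 0.911.

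**Visit 1 less correlated with week 12 than Visit 2 is.**

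| a | b | c | variance falls | SE falls |
|---|---|---|---|---|
| 0.90 | 0.80 | 0.78 | 5.3% | 2.7% |
| 0.90 | 0.80 | 0.75 | 1.3% | 0.7% |
| 0.90 | 0.80 | 0.72 | 0% | 0% |
| 0.80 | 0.70 | 0.65 | 4.4% | 2.2% |

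For the second row: (0.75 - 0.72)² = 0.0009; 0.19 × 0.36 = 0.0684; 0.0009/0.0684 = 0.013.

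**Stable level plus drift plus noise.** Assumed on the log scale: between-patient SD 0.7 to 0.9, visit-to-visit SD 0.2 to 0.4, drift SD 0 to 0.35, and Visit 1 two weeks before baseline. With selection on the Visit 1 value included, the simulated variance falls by 6.7% to 23.2%. The SE therefore falls by 1 - √0.933 = 3% to 1 - √0.768 = 12%. A less favourable set (stable SD 0.7, visit-to-visit SD 0.1 to 0.2, drift SD 0.5 with a time constant of 6 to 12 weeks, no selection) gives 2.0% to 4.8% in variance, or 1.0% to 2.4% in SE.

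**Selection at entry.** Simulated trials with 150 per group, Visit 1 truncated at 450 pg/ml, an assumed log-SD of 1.0 and assumed medians of 600 to 2000 pg/ml gave an SE reduction of about 6% to 11% at equal correlations of 0.7 to 0.9. Without truncation it is 9% to 12%. Under purely time-decaying correlation the gain was nil.

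**Bias.** With no true effect, both models gave treatment estimates centred on zero (means between -0.0022 and 0.0021 on the log scale).

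**The case against.** The case for leaving the plan alone is fair in several respects. Protocol and SAP agree on the baseline rule and on the model, adjusting for one baseline is valid, and the endpoint is exploratory. The size of any gain cannot be read from the documents. All of this stands, and it makes the change optional.

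Four stronger readings are tempting, and the documents do not support them:

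- **Precision is certainly lost.** This cannot be asserted without correlations that the documents do not give. The loss is zero when c = ab. That case needs Visit 2 to carry everything Visit 1 knows, which is unlikely where visit-to-visit noise exists in patients required to have stable chronic heart failure. The 1.3% example is also near the low end. With an assumed 14-day gap it has correlation falling by 0.10 over 70 days and then by 0.05 over the next 14. At a constant rate the second fall would be 0.02, so c = 0.78 and the gain is 5.3%.
- **The screening value is discarded.** It decides entry, and under SAP 6.7 it becomes the baseline when Visit 2 is missing. SAP 6.7 also rules out a laboratory sample taken after treatment start as baseline, which leads to the same fallback.
- **A distinct second covariate exists for every patient.** In those fallback patients it does not. Protocol 3.3 also allows one NT-proBNP re-test, so more than one screening value can exist.
- **The creatinine and eGFR rule shows an inconsistency.** It is a stated exception in both documents, and it averages values into one baseline. It shows that using all pre-treatment values was considered for one parameter, but it is no precedent for a second covariate.

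**Conclusion.** The point holds as an efficiency refinement, at optional priority. The planned NT-proBNP analysis is valid and unbiased, and there is no contradiction between the documents. It probably gives a somewhat wider interval than the collected data allow. Under the assumed correlations and variances, the second covariate would lower residual variance by about 1% to 23%, with nothing gained in the limiting case. Interval width is the relevant scale, and there the range is about 1% to 12%. Expressing the gain as extra patients would make it look larger than what a reader of the interval would see. Type I error, the sample size and the primary and key secondary conclusions do not depend on this choice.

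**What to change.** In SAP 7.5.2, and correspondingly in protocol 7.3.2 and the synopsis, add log-transformed Visit 1 NT-proBNP and its interaction with visit as a second covariate beside the existing baseline. Keep change from the Visit 2 baseline as the response. Averaging the two values into a new baseline would bring the value selected at entry into the reported change, and with it regression to the mean.

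Add two rules:

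- If the screening sample was re-tested, use the last Visit 1 central-laboratory value.
- If no valid Visit 2 value exists, the Visit 1 value fills both covariates, so that no patient is dropped.

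The cost is one covariate with its visit interaction (two parameters for two post-baseline visits, with about 300 patients) and two sentences in the SAP. No new samples, visits or patients are needed. The change should be fixed before unblinding.

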## FLOW CHART

Trial Period	Screening*	Randomized Treatment Period				FU Period
		1	2	3	4 (EOT)	
Visit	1	2	3	4 (EOT)	Early Discontinuation on Visit 	FU Visit
Trial week	-3	1	6	12		EOT/early d/c + 7 days
Days of treatment	-21 to -4	1	43	85		
Time Window	-	-	±7	±7		+7
Informed consent	X					
In/exclusion criteria	X	X				
Demographics	X					
Medical history/Concomitant diagnoses	X					
Vital signs 	X	X	X	X	X	X
Physical examination	X	X		X	X	
Height	X					
Weight	X	X		X	X	
Urine Pregnancy test 	X	X	X	X	X	
HbA1c		X		X	X	
eGFR (CKD-EPIcr formula)	X 	X	X	X	X	X
Safety lab: blood tests	X 3*	X	X 	X	X	X
Safety lab: urinalysis including ketones	X 	X	X	X	X	X
ECG exam 	X 			X	X	
Echocardiogram 	X					
NT-proBNP	X 	X	X	X	X	
6 min walk test 	X 	X 	X	X 	X	
Concomitant therapy	X	X	X	X	X	X
Adverse events	X	X	X	X	X	X
KCCQ 		X	X	X	X	
CHQ-SAS 		X	X	X	X	
Clinical Congestion Score		X	X	X	X	
Patient Global Impression of Severity of Heart Failure Symptoms 		X	X	X	X	
Patient Global Impression of Severity of Dyspnea 		X	X	X	X	
Patient Global Impression of Change in Heart Failure Symptoms 			X	X	X	

Trial Period	Screening*	Randomized Treatment Period				FU Period
Visit	1	2	3	4 (EOT)	Early Discontinuation on Visit 	FU Visit
Trial week	-3	1	6	12		EOT/early d/c + 7 days
Days of treatment	-21 to -4	1	43	85		
Time Window	-	-	±7	±7		+7
Patient Global Impression of Change in Dyspnea 			X	X	X	
Clinician Global Impression of Severity of CHF		X	X	X	X	
Clinician Global Impression of Change in CHF Severity			X	X	X	
NYHA Classification	X	X	X	X	X	
HCRU		X	X	X	X	
Randomization (IRT)		X				
Dispense trial medication		X	X			
Return medication / Medication compliance check			X	X	X	

\* The screening procedures can be performed on different days within the time window. Specifically it is recommended to have the NT-proBNP and safety lab measures (via central lab) measured as first step, especially in patients with no previous natriuretic peptide value available from clinical routine assessment in the past 6 months (refer to [section 6.2.1](#)). The baseline rhythm (e.g. sinus rhythm, AF) of the patient must be clarified (i.e. ECG) and documented at the time the NT-proBNP sample is collected.

1. Blood pressure and heart rate will be measured with the patient seated and rested for at least 5 minutes.
2. For female patients of child-bearing potential, local urine pregnancy test should be performed.
3. For the screening Visit 1, the safety laboratory is limited to liver transaminases, alkaline phosphatase, haemoglobin, serum creatinine, eGFR calculation. Patients do not have to be fasting.
4. For Visit 3, the safety laboratory is limited to liver transaminases, bilirubin and serum creatinine, eGFR calculation
5. A 12-lead ECG will be performed at screening and EOT visits. For this 12-lead ECG, the interpretation of the tracing must be made locally by the investigator or designee. In case of any cardiac symptom (indicating rhythm disorders or cardiac ischaemia), additional 12-lead ECG(s) should be done and any abnormal findings will be reported as AEs.
6. An echocardiogram should be performed on all patients at Visit 1 to assess left ventricular ejection fraction (LVEF) for eligibility.
7. 6MWT to be performed by qualified and experienced personnel. The assessments should be performed by the same qualified and experienced personnel at all visits, where possible.

- Testing of the 6MWT at each clinic visit should be preferably performed about the same time of day to minimize intraday variability. Prior to performing the 6MWT, the relative contraindications to exercise should be assessed as per [appendix 10.1.3](#). Heart rate and blood pressure will be measured before exercise, at end-exercise, five minutes after termination of exercise and when, for clinical reasons, it is required.
8. One 6 minute walk test (6MWT) will be performed at the screening visit. The 6MWT will be performed after vital signs have been captured and prior to any other study procedures at this visit. If the distance walked is > 350m the patient will be considered a screen failure.
  9. Two 6 minute walk tests will be performed at visits 2 and 4 at least 1 hour apart. The largest distance measured will be used for the analysis. If at Visit 2 the distance walked on any test is > 350m or the largest distance walked is < 100m the patient will be considered a screen failure.
  10. For the order of completion of patient reported outcome measures please refer to [section 6.2.2](#).
  11. Patients who prematurely discontinue from trial medication will be required to return to the study site as soon as possible after treatment discontinuation for the early discontinuation visit and the follow up visit. In addition, the patient should return to clinic for their regularly scheduled week 12 study visit as outlined in [section 3.3.4.1](#).

